Statistical Analysis Plan

Protocol Title

Measurement of Oxygen Saturation in healthy human volunteers before, during and after hyperemic events using Multi-Modal Techniques: Spatial Frequency Domain Imaging (SFDI), transcutaneous oxygen measurement (TCOM), Pulse Oximeter, and Apple Watch.

Principal Investigator:

[name]. Assistant Professor, Indiana Center for Regenerative Medicine and Engineering at Indiana University Department of Surgery, Division of Plastic Surgery School of Medicine, Indiana University Analysis will be performed based on search of answers for the questions designed.

Q1: What are the correlations between the measurements we've taken? Are those correlations significant?

The repeated measures correlations for the measurements. Use repeated measures correlation because we have repeated measures for our data (we get values for each measurement four separate times).

Q2: What are the differences between males' and females' measurements, over time?

We have 20 subjects (13 male, 7 female). We have 5 parameters for each subject: StO2, HbO2, HbR, HbT1, and HBT2. Each measurement will be recorded at 4 time points: baseline, occlusion, reactive hyperemia, and recovery. Plots showing how subjects' measurements changed over time will be obtained. The mean measurement value for males and females, over time will be obtained. Hypothesized that males' and females' measurements follow similar patterns over time. StO2 for males will have higher average HbO2, HbR, HbT1 and HbT2 measurements than females, over all time points compared to females.

Q3. Is this male/female gap in measurements statistically significant, though?

To answer this, I fit multivariate linear regression models at each time point. Results of multivariate linear regression models, for each time point will be obtained. Multivariate models are basically just regression models with multiple outcome variables; in this case, the outcomes are the 5 measurements. The regression coefficients for the intercepts are basically the estimated average measurement for males, for that measurement, at that time point; the p values for the intercepts don't really matter. The regression coefficients for female is just the estimated average difference between males and females, for that measurement, at that time point.

Example:

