For StO2 at time 1, it's estimated that males have an StO2 value of 62, with a 95% confidence interval of 54 to 70. It's estimated that females have StO2 values at time 1 that are 4 higher than males, on average [95% confidence interval ranges from 11 lower than males, to 19 higher than males]. That confidence interval [-11 to 19] contains 0, so there's a strong enough possibility that the difference between male and female StO2 values at time 1 is 0 (i.e. there's no difference). Because of that, the p value for Time 1/StO2/Female is 0.581, which is greater than .05, which

means we can't reject the idea the females and males have the same StO2 values at time 1.

Q2: Instead of gender, what about differences between skin type (II and III vs. IV)?

Plot of measurements over time for subjects with skin type II and III vs. skin type IV will be analyzed. The data represent the mean measurement value for skin types 2 and 3 vs skin type 4, over time. Based on the above plots, it appears that (on average) those with skin type 4 have lower StO2 and HbO2 over time, compared to those with skin type 2 and 3. Skin type 4s appear to have higher HbR and HbT1 over time, compared to skin type II and III. There's a lot of variation in HBT2 over time, and both skin type groups have similar mean values over time. Like for gender, I fit separate multivariate linear regression models for each time point. The regression coefficients for the intercepts are basically the estimated average measurement for the skin type II + III group, for that measurement, at that time point; the p values for the intercepts don't really matter. The regression coefficients for skin type IV is just the estimated average difference between 4s and 2s + 3s, for that measurement, at that time point.

Example:

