For StO2 at time 1, it's estimated that type 2s and 3s have an StO2 value of 71, with a 95% confidence interval of 63 to 78. It's estimated that type 4s have StO2 values at time 1 that are 20 lower than type 2s and 3s, on average [95% confidence interval ranges from 33 lower than 2s and 3s, to 7 lower than 2s and 3s]. That confidence interval [-33 to -7] does not contain 0, meaning we're confident that the difference between 4s and 2s/3s is not 0. Because of that, the p value for Time 1/StO2/Female is 0.004, which is less than .05, which means we can reject the idea that 4s and 2s/3s have the same StO2 values at time 1. Most of the 5 measurements are correlated with one another. Females and males had similar measurements at baseline, but started to differ in HbO2, HbR, HbT1, and HbT2 from inflation onwards. Those with skin type 4 had lower StO2, higher HbR, and higher HbT1 compared to those with skin type 2 and 3, at all-time points; the two groups didn't significantly differ in regard to HbO2 and HbT2 at any time.

Abbreviation StO2= tissue oxygen saturation HbO2=oxy hemoglobin HbR= deoxy hemoglobin HbT1= superficial perfusion hemoglobin HbT2= deep perfusion hemoglobin TCOM=trans-cutaneous oxygen measurement

SFDI=spatial frequency domain imaging

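### The SAP concludes that males and females were similar at baseline, but its printed StO2 interval of -11 to 19 points is inconclusive

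*SAP*

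**What the plan says.** All the relevant text is in the SAP.

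- **Sample (first Q2).** "We have 20 subjects (13 male, 7 female".
- **Sex example (under Q3).** The fitted result is that "males have an StO2 value of 62, with a 95% confidence interval of 54 to 70" and that "females have StO2 values at time 1 that are 4 higher than males, on average", where the "95% confidence interval ranges from 11 lower than males, to 19 higher than males". The SAP reads this as follows: "so there's a strong enough possibility that the difference between male and female StO2 values at time 1 is 0 (i.e. there's no difference". It adds that "the p value for Time 1/StO2/Female is 0.581, which is greater than .05", and ends by saying that equality of the sexes cannot be rejected.
- **Closing summary (end of the skin-type example).** Males and females are described as similar at baseline and as diverging in HbO2, HbR, HbT1 and HbT2 from cuff inflation onwards. For skin type IV against II and III, it reports differences in StO2, HbR and HbT1 at every time point, and for the rest that "the two groups didn't significantly differ in regard to HbO2 and HbT2 at any time".
- **Skin-type plots (second Q2).** Type IV appears lower on HbO2. HbT2 is described as highly variable, and "both skin type groups have similar mean values over time".

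Neither document gives a power calculation, a smallest important difference or a similarity margin. Protocol section 9.0 (Statistical Considerations) plans only means and standard errors.

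**The concern.** An interval that contains 0 shows that zero is one of the values the data allow. It says nothing special in favour of zero, and this interval allows a wide range of other values. The comment in the sex example blurs that distinction, and the closing summary loses it: a test that failed to reject becomes a positive statement of similarity.

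A reader who sees only the summary would take it that the sexes start level and separate once the cuff is inflated. The printed StO2 interval does not establish the first half of that account, and no intervals are printed for the other four measurements at baseline.

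The same caution applies, more mildly, to skin type. Possible skin-colour bias in optical oximeters is an exploratory objective (Protocol section 1.3), and for a bias question a missed difference is the error to guard against. HbO2 appears lower in type IV on the plots, yet the summary closes it with a bare statement of non-significance and no estimate.

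**Working it through.** **Inputs, all from the SAP.** Sex split 13 and 7. Sex difference in StO2 at time 1: +4, CI -11 to 19, p = 0.581. Male mean 62, CI 54 to 70. Skin-type difference in StO2 at time 1: -20, CI -33 to -7, p = 0.004 (printed under a Female label). Assumptions: time 1 is baseline (first in the SAP's list of time points), all 20 subjects contribute, and each model has one two-level factor, so df = 20 - 2 = 18 and t(0.975) = 2.101.

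**Step 1: reproduce the printed p values.**
- Sex: half-width = (19 + 11)/2 = 15; SE = 15/2.101 = 7.14; t = 4/7.14 = 0.56; p = 0.582 against the printed 0.581.
- Skin type: half-width = (33 - 7)/2 = 13; SE = 13/2.101 = 6.19; t = 20/6.19 = 3.23; p = 0.0046 against the printed 0.004. Rounding of the inputs allows 0.003 to 0.007.

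Both agree within rounding, so the implied standard errors can be used.

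**Step 2: what the sex interval allows.** Against a male mean of 62, -11/62 = -18% and 19/62 = +31%. The data are compatible with females being about a fifth lower or nearly a third higher.

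**Step 3: how often a real sex gap would be non-significant.** Two-sided 5% test, noncentral t with 18 df and noncentrality = true gap/SE.

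| True StO2 gap | Noncentrality | Power | Non-significant |
|---|---|---|---|
| 10 points | 10/7.14 = 1.40 | 0.26 | 74% |
| 15 points | 15/7.14 = 2.10 | 0.51 | 49% |

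At 80% power (a conventional level, not one from the documents) the required noncentrality is 2.96, so the detectable gap is 2.96 × 7.14 = about 21 points.

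**Step 4: sensitivity to the SD.** The difference interval implies SD = 7.14/√(1/13 + 1/7) = 7.14/0.469 = 15.2. The male interval implies SD = (8/2.101) × √13 = 13.7. The two do not match exactly for a 13:7 pooled-variance model. Over SDs of 12.9 to 15.7, which cover both sources with rounding, a 10-point gap is non-significant 65% to 75% of the time and a 15-point gap 35% to 51%. At SD 13.7 the 80%-power gap is about 19 points. The conclusion does not change.

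**Step 5: skin type, StO2 only.** From SE 6.19 and 18 df, a true 10-point gap has noncentrality 10/6.19 = 1.62 and power 0.33, so it would be missed about 67% of the time. The 80%-power gap is 2.96 × 6.19 = about 18 points. This uses the printed interval and needs no group sizes, which the SAP does not state. It cannot be carried over to HbO2 or HbT2, for which no intervals are printed.

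**The case against.** The strongest reply is that the SAP's formal decision is right. The sex example ends with a proper fail-to-reject statement, and the parenthesis in the comment only spells out what a zero difference means. That stands: the SAP does not adopt a rule that an interval containing 0 proves equality. It does not rescue the closing summary, which drops the cautious wording and calls the sexes similar.

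A reader might infer more: that the SAP would pass off large skin-type differences as similarity and so claim that the devices are free of skin-colour bias. The documents do not support this, for four reasons.

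- The 13 and 7 split is by sex. The skin-type group sizes are not given.
- The remark that HbT2 means are alike is a reading of plots, made before the models are mentioned and next to a warning about variation. It did not come from a confidence interval.
- The summary wording for HbO2 and HbT2 is a literal report of tests, and the SAP itself says that HbO2 looks lower in type IV.
- Nothing in the SAP claims absence of bias. It reports a 20-point StO2 difference and differences in HbR and HbT1.

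It is also tempting to set the 19-point upper limit for sex beside the 20-point skin-type estimate. That compares a confidence limit with a point estimate, and the argument here does not need it.

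Two further replies have some force. Sex is not a protocol objective, which limits the consequence. And the 10- and 15-point gaps are illustrations, because the documents name no important difference.

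**Conclusion.** The point holds for sex. The SAP's own StO2 interval is inconclusive and does not support the baseline similarity statement: at its implied standard error, a true 10-point gap would be non-significant about 74% of the time and a 15-point gap about 49%. For the other four baseline measurements, the statement cannot be checked from what is printed.

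For skin type the point is narrower. Reporting HbO2 and HbT2 as not significantly different is accurate but incomplete without estimates and intervals. The 67% figure for a 10-point gap gives a sense of the precision for StO2 only.

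The figures assume pooled variance, 18 degrees of freedom and complete data on 20 subjects. The matter is one of interpretation and reporting; the fitted models are not in question here. It is worth correcting because it changes a stated conclusion at almost no cost.

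**What to change.** 1. **Sex example under SAP Q3.** Replace the comment on the interval with: *the interval includes 0, so the result is inconclusive: the data are compatible with females being 11 points lower to 19 points higher.* Keep the sentence saying that equality cannot be rejected.
2. **Closing summary, sex at baseline.** Remove the word *similar*. Give the female-minus-male estimate and 95% CI for each of the five measurements, and for those whose interval includes 0 state: *no difference was shown; inconclusive.*
3. **Closing summary, skin type.** Keep the report of non-significance for HbO2 and HbT2, add the estimates and 95% CIs at each time point, and state the number of subjects in each skin-type group.

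Do not add an equivalence margin for these data. The SAP already prints fitted results and states conclusions in the past tense, so a margin chosen now would not be prespecified.

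The cost is SAP wording and a table of intervals that the fitted models already provide. No new data or models are needed. The downside is that some conclusions become less definite.

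### Sex and skin type are tested only in separate one-factor models; report the cross-table and mutually adjusted estimates, chiefly for HbR and HbT1

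*SAP*

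**What the plan says.** The SAP states the sex split: "We have 20 subjects (13 male, 7 female". Under Q3 it fits, at each time point, a regression of the five SFDI outcomes in which the intercept is read as the male mean and the one other coefficient as the female-minus-male difference. Sex is therefore the only factor.

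The second Q2 replaces that factor: "Instead of gender, what about differences between skin type (II and III vs. IV". The method carries over: "Like for gender, I fit separate multivariate linear regression models for each time point". In that sentence the word for separateness refers to time points. The one-factor reading rests on the replacement of sex by skin type and on the intercept, which is now the plain II/III mean.

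The worked examples are for StO2 at time 1. For sex, "females have StO2 values at time 1 that are 4 higher than males, on average" (CI -11 to 19, p = 0.581). For skin type, "type 4s have StO2 values at time 1 that are 20 lower than type 2s and 3s" (CI -33 to -7, p = 0.004).

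The closing summary says the sexes "started to differ in HbO2, HbR, HbT1, and HbT2 from inflation onwards". It then says: "Those with skin type 4 had lower StO2, higher HbR, and higher HbT1 compared to those with skin type 2 and 3", at every time point. Neither document gives a two-factor model, the skin-type group sizes or the sex-by-skin-type table.

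**The concern.** HbR and HbT1 are the only outcomes that appear in both lists of differences. The SAP hypothesises under the first Q2 that "males will have higher average HbO2, HbR, HbT1 and HbT2 measurements than females", and it reports HbR and HbT1 as higher in type IV. If both directions hold, an excess of type IV among the men would inflate both contrasts, and an excess among the women would shrink both. With 13 men and 7 women, some imbalance is easy to get. A reader cannot tell whether the sex differences in HbR and HbT1 stand apart from skin type, or the reverse, although both factors were recorded for every subject.

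The stakes are limited. Skin colour is a tertiary objective (protocol section 1.3), and sex is not a protocol objective.

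**Working it through.** **1. Reproduce the SAP's p values as unadjusted tests.** With 20 subjects and two coefficients, df = 18 and t(0.975) = 2.101.

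- Sex: half-width (19 + 11)/2 = 15; SE = 15/2.101 = 7.14; t = 4/7.14 = 0.56; p = 0.582 (stated 0.581).
- Skin type: half-width (33 - 7)/2 = 13; SE = 13/2.101 = 6.19; t = -20/6.19 = -3.23; p = 0.0046 (stated 0.004, within rounding).

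Both examples match a plain two-group comparison.

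**2. Infer the number of type IV subjects, n4, which is not stated.**

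- From means: the overall mean from the sex example is 62 + 4 × 7/20 = 63.4. From the skin-type example it is 71 - 20 × n4/20 = 71 - n4. Equating them gives n4 = 7.6.
- From CI widths: the II/III mean has half-width (78 - 63)/2 = 7.5. (13/7.5)² = 3.00 = 20/n4 gives n4 = 6.7.

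I assume 7 and tried 6 to 8.

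**3. Obtain the two-factor estimates from the two one-factor contrasts.** Let d be the share of type IV among women minus the share among men. Let e be the share of women in type IV minus the share in II/III. Then

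- bSex = (4 + 20d)/(1 - de)
- bSkin = (-20 - 4e)/(1 - de)
- variance inflation factor (VIF) = 1/(1 - de)

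With n4 = 7, d = e. Example with one type IV woman: d = 1/7 - 6/13 = -0.319, so bSex = (4 - 6.37)/(1 - 0.102) = -2.6.

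For the p values, residual df = 17. The total sum of squares at time 1 comes from either printed CI:

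- Sex: residual SD = 7.14/√(1/13 + 1/7) = 15.23; total = 18 × 15.23² + 4² × 13 × 7/20 = 4248.
- Skin type: residual SD = 6.19/√(1/13 + 1/7) = 13.20; total = 18 × 13.20² + 20² × 13 × 7/20 = 4956.

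The two totals differ partly because the printed figures are rounded, so p for sex is given as a range.

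| Type IV women (of 7) | d | Adjusted sex difference | p | Adjusted skin-type difference | VIF | Chance of this table |
|---|---|---|---|---|---|---|
| 1 | -0.319 | -2.6 | 0.66-0.70 | -20.8 | 1.11 | 0.155 |
| 2 | -0.099 | +2.0 | 0.72-0.75 | -19.8 | 1.01 | 0.349 |
| 3 | 0.121 | +6.5 | 0.25-0.31 | -20.8 | 1.01 | 0.323 |
| 4 | 0.341 | +12.2 | 0.03-0.06 | -24.2 | 1.13 | 0.129 |

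Every skin-type p in the table is below 0.007. The last column is the hypergeometric probability if sex and skin type are unrelated. The extreme tables, 0 or 5 type IV women, have probability about 0.02 each and give sex differences of -9.5 and +22.2. Across all tables compatible with the printed figures for n4 = 6 to 8, the skin-type difference runs from -19.8 to -42.7, always with p at or below 0.007.

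**4. How likely is a material imbalance?** Two or three type IV women has probability 0.349 + 0.323 = 0.67, and the unadjusted sex contrast then differs from the adjusted one by only 4 - 2.0 = +2.0 or 4 - 6.5 = -2.5. A gap of 30 percentage points or more in type IV share has the remaining probability, 33%.

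**5. HbR and HbT1.** No estimates are printed. With n4 = 7, a pure effect of one factor appears in the other factor's contrast at |d| times its size: 10% (2/7 v 5/13), 12% (3/7 v 4/13), 32% (1/7 v 6/13) or 34% (4/7 v 3/13).

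**The case against.** The questions are descriptive, and an unadjusted difference answers a descriptive question correctly; the SAP nowhere says that the two effects are independent. The outcomes named in the heading cannot be recalculated. The figure shown to be fragile is a time-1 StO2 sex contrast that the SAP itself reports as not significant. The summary does not say which sex is higher, so the direction of any bias is borrowed from a hypothesis. The reported patterns also differ: skin type separates HbR and HbT1 at baseline while the sexes are alike there, and sex separates HbO2 and HbT2 while skin type does not. That argues against the two factors nearly coinciding. Finally, adjustment comes after results are known, adds up to 5 × 4 × 2 = 40 coefficients, and may rest on a cell of one to four women.

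Much of this stands as a limit on weight. Confounding is not shown, and the figures above are illustrations. They also rest on rounded inputs: in the sex example the ratio of half-widths is 15/8 = 1.875 (1.71 to 2.07 allowing for rounding), while 13 v 7 implies √(1 + 13/7) = 1.69, just outside. The number analysed per group therefore needs confirming too.

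It does not remove the point. The SAP lists HbR and HbT1 as differing by both factors and gives the reader no means of separating them. A small cell is a reason to print the table, not to omit it.

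**Conclusion.** The concern holds. Each contrast is unadjusted for a factor already collected, and two outcomes are claimed for both factors. Assuming 7 type IV subjects and additive effects, the time-1 StO2 sex difference of +4 could lie between -2.6 and +12.2 with 1 to 4 type IV women. Only the last case comes near p = 0.05, and in the likelier tables the change is 2 to 2.5 points. The time-1 StO2 skin-type conclusion is robust in every feasible table. For HbR and HbT1, between a tenth and a third of one factor's effect could appear in the other's contrast; the actual amount is unknown without the cross-table. This is a worthwhile, inexpensive improvement to exploratory results, and confidence in its practical importance is moderate.

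**What to change.** Report the sex-by-skin-type counts and the number analysed in each cell. Fit outcome on sex plus skin type at each time point, or include both factors in a repeated-measures model. Show the mutually adjusted differences with confidence intervals beside the unadjusted ones, labelled exploratory, and base any claim of a separate sex or skin-type effect on the adjusted estimates. If the two factors nearly coincide, state that their effects cannot be separated.

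No new data are needed. Residual df falls from 18 to 17, so t goes from 2.101 to 2.110 and intervals widen by about 0.4%, before variance inflation. At a VIF of 1.13 the factor is 1.004 × √1.13 = 1.067, so the skin-type half-width of 13 becomes about 13.9. If no woman is type IV, the VIF is 1.41 and the factor is 1.004 × √1.41 = 1.192, giving about 15.5. Both ignore any change in residual SD. The model cannot be fitted if the factors coincide, and an additive model does not address a sex-by-skin-type interaction.

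### The sex and skin-type regressions assume equal spread in groups of unequal size, and the SAP neither checks that assumption nor protects against its failure

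*SAP*

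**What the plan says.** The sex analysis is in SAP Q3: "I fit multivariate linear regression models at each time point". The skin-type analysis, under the second item numbered Q2, repeats it: "Like for gender, I fit separate multivariate linear regression models for each time point". In both, the intercept is the reference group's mean and the single coefficient is the difference between groups. There are five outcomes (StO2, HbO2, HbR, HbT1, HbT2) at four time points.

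Group sizes are given for sex, "We have 20 subjects (13 male, 7 female", but not for skin type, where the SAP gives only the grouping: "what about differences between skin type (II and III vs. IV". The sex example is StO2 at time 1: "males have an StO2 value of 62, with a 95% confidence interval of 54 to 70", with a female-minus-male difference of 4, "95% confidence interval ranges from 11 lower than males, to 19 higher than males", and "the p value for Time 1/StO2/Female is 0.581, which is greater than .05". The skin-type example gives 71 (63 to 78) for types II and III, a difference of -20 (-33 to -7) and p = 0.004.

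The closing summary draws conclusions from these models, for instance "Those with skin type 4 had lower StO2, higher HbR, and higher HbT1" relative to types II and III at every time point. The SAP mentions no unequal-variance method, robust standard error, check of spread or group SD.

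**The concern.** Fitting five outcomes together does not change the coefficient-level results. For each outcome, the coefficient's interval and p value are those of an equal-variance two-sample t test. That test tolerates unequal spread when the groups are the same size. It does not when they are as unequal as 13 and 7, because the pooled variance is then dominated by the larger group. If the smaller group is the more variable, the standard error is too small. If the larger group is, the standard error is too large.

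The same assumption sits behind 5 outcomes x 4 time points x 2 groupings = 40 coefficients. The skin-type results bear on the protocol's exploratory objective about skin-colour bias. A reader given means and p values without group SDs cannot judge whether the assumption is reasonable.

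**Working it through.** **1. The SAP's own figures.** With 20 subjects and two groups there are 18 residual degrees of freedom, and t(0.975, 18) = 2.101. SE = half-width / 2.101, and p = 2 x P(T18 > |difference| / SE).

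- Sex: half-width 15, SE = 15/2.101 = 7.14, t = 4/7.14 = 0.56, p = 0.582 (stated 0.581).
- Skin type: half-width 13, SE = 13/2.101 = 6.19, t = 20/6.19 = 3.23, p = 0.0046. Rounding of the printed figures allows 0.0029 to 0.0071 (stated 0.004).

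Both agree with ordinary regression on 18 df. Given the rounding, this is consistent with a pooled model but does not prove one.

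**2. Skin-type group sizes.** In a pooled model the difference half-width equals the intercept half-width x sqrt(1 + n1/n2), where n1 is the reference group.

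- Skin type: the half-widths are 7.5 (7 to 8 after rounding) and 13 (12.5 to 13.5). So n1/n2 lies between (12.5/8)^2 - 1 = 1.44 and (13.5/7)^2 - 1 = 2.72. If N = 20, that allows 12/8, 13/7 or 14/6, with type IV the smaller group. This is an inference.
- Sex: 8 x sqrt(1 + 13/7) = 13.5 (12.7 to 14.4 after rounding), against a printed 15 (14.5 to 15.5). The printed intervals narrowly miss a pooled 13/7 model and would fit 14/6 or 15/5. This does not show unequal variance. It does mean that the analysed group sizes and the variance method should be checked.

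**3. Effect of unequal spread.** Let r be the smaller group's SD divided by the larger group's. The documents give no group SDs, so r from 0.5 to 2 is an assumed range. In units of the larger group's variance, the expected pooled squared SE is [(n1-1) + (n2-1)r^2]/(n1+n2-2) x (1/n1 + 1/n2), and the true one is 1/n1 + r^2/n2. At 13/7:

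- r = 2: pooled (36/18) x 0.2198 = 0.440, true 0.648, SE ratio sqrt(0.440/0.648) = 0.82.
- r = 0.5: pooled (13.5/18) x 0.2198 = 0.165, true 0.113, SE ratio 1.21.

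Rejection rates of a nominal 5% two-sided test with no true difference (200,000 simulated normal data sets per cell):

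| r | Pooled 13/7 | Welch 13/7 | Pooled 12/8 | Pooled 14/6 |
|---|---|---|---|---|
| 0.5 | 2.3% | 4.9% | 3.1% | 1.6% |
| 0.67 | 3.0% | 4.9% | 3.7% | 2.5% |
| 1 | 5.0% | 5.0% | 5.0% | 5.0% |
| 1.5 | 8.2% | 5.2% | 7.2% | 9.4% |
| 2 | 10.8% | 5.2% | 8.8% | 13.1% |

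For given SDs, interval coverage does not depend on the true difference, so it is 100% minus the rejection rate. At 13/7 the pooled 95% interval covers about 92% at r = 1.5 and about 97% at r = 0.67.

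**4. The worked examples under Welch.** Hold the pooled SD at the value implied by the printed interval and vary r from 0.5 to 2.

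- Sex (13/7): p = 0.51 to 0.66.
- Skin type: p = 0.001 to 0.030 at 13/7 and 0.002 to 0.019 at 12/8. At 14/6 and r = 2, the pooled SD is 6.19/sqrt(1/14 + 1/6) = 12.68, the Welch SE is 8.05 on 6.1 df, t = 20/8.05 = 2.49 and p = 0.047.

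Neither example changes side of 0.05, although the last case comes close.

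**The case against.** The strongest objection is that nothing in the documents shows the spreads to differ. The natural reason to expect it is that the spread of concentrations and percentages often rises with the mean. But then groups with equal means have equal spreads, and the pooled test keeps its 5% error rate. That stands against any claim of inflated false positives from this mechanism alone. It does not rescue the intervals: if the means differ and spread follows them, the pooled interval still has the wrong coverage.

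A reader might infer that the error runs in opposite directions, too cautious for sex and too liberal for skin type. The documents do not support that. Direction depends only on which group is more variable, which is not reported. Even if spread rose with the mean, HbO2 would go the same way in both analyses, since males (hypothesised) and types II and III (as plotted) are the higher groups and appear to be the larger ones. StO2 is lower in type IV, so there the skin-type test would be too cautious.

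A reader might also infer that the skin-type findings for HbR and HbT1 are probably false positives, or that sex differences are being hidden. Neither follows. No SDs or p values are printed for those outcomes, and the closing summary already reports sex differences from inflation onwards.

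The SD ratios of 1.5 and 2 are assumptions. The only printed group means, both for StO2, differ by factors of 66/62 = 1.06 and 71/51 = 1.39. SD ratios of that size, with the smaller group more variable, would put the pooled error at about 5% and 7%. This limits the likely size of the problem for StO2 and says nothing about the other four outcomes.

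Finally, Welch can cost more than a little power. With SD proportional to the mean (coefficient of variation 0.3) and the smaller group's mean 1.5 times the larger's, power falls from 78% to 65%. But there r = 1.5, where the pooled test's nominal 5% is really about 8% and its interval covers about 92%, so part of the apparent advantage comes from that miscalibration.

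**Conclusion.** The point holds as a conditional one. The planned regressions assume one residual variance per outcome, the sex groups are 13 and 7, the skin-type groups are probably about as unequal, and the SAP has no safeguard. If the spreads differ by a factor of 1.5 to 2, the true error rate at 13/7 is about 8% to 11% or about 3% to 2%, depending on which group is more variable, and interval coverage is off to match. Whether this happens, in which direction and by how much cannot be told from the documents for either comparison.

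The conclusion rests on reading the models as ordinary least squares, on approximately normal outcomes, on the assumed SD ratios and, for skin type, on inferred group sizes. The two worked examples stand. This is a low-cost improvement to the plan, not a demonstrated mistake in a result.

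**What to change.** State in Q3 and in the skin-type section that the interval and p value for each group coefficient use unequal-variance inference: Welch's method for the single-indicator models, or HC3 robust standard errors if covariates are added. Print each group's n and SD beside its mean, for every outcome and time point. That would also supply the missing skin-type group sizes and allow the mismatch in the sex example's intervals to be resolved.

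The work is one SAP sentence, one model option and two extra table columns. If the spreads are in fact equal, intervals are slightly wider and power falls by about 2 to 3 percentage points at 13/7, and by up to about 5 points at 14/6.
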